	antifibrotic treatment between October 1, 2014 and April 30, 2018. Patients will be divided into three mutually exclusive cohorts: (1) nintedanib initiators; (2) pirfenidone initiators; and (3) control cohort who received no prescription antifibrotic treatment during selection window.										
Variables:	The following demographic and clinical characteristics as well as medical interventions for IPF during the 12-month baseline period (pre-treatment) will be evaluated and compared between cohorts 
 Demographic characteristics (e.g., age, gender, race/ethnicity, geographic region, insurance type) Clinical characteristics (e.g., selected comorbidities, baseline weight and body mass index [BMI], blood pressure, smoking status, laboratory measures, pulmonary function tests) Pharmacological interventions (e.g., index medication dose, time from the earliest diagnosis of IPF to index medication, other IPF treatments, bronchodilators, corticosteroids) Non-pharmacological interventions (e.g., surgical procedures, supportive therapies, diagnostic procedures) 										
Data sources:	GE Centricity EMR database from October 2013 to April 2018										
Study size:	A preliminary analysis identified 868 IPF patients with pirfenidone, 615 patients with nintedanib, and about 10,000 untreated patients.										
Data analysis:	Patient demographic and clinical characteristics will be described using descriptive analyses. Counts and percentages for categorical variables and measures of central tendency (mean, median, standard deviation [SD], and min/max) for continuous variables will be reported. Differences between the treatment cohorts (compared to each other and to untreated patients) will be assessed using absolute standardized differences and p-values. The probabilities of receiving one treatment over another will be tested by propensity scores and using multivariable logistic regression adjusted for key baseline characteristics. The similarities and differences between two treatment cohorts will be assessed using balance diagnostics tests. A stratified descriptive analysis will also be conducted at different time points to assess if the characteristics of the two exposures changes over time.										

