7. RATIONALE AND BACKGROUND

Idiopathic Pulmonary Fibrosis (IPF) is a specific form of chronic, progressive fibrosing interstitial pneumonia of unknown cause, occurring primarily in older adults, and limited to the lungs.¹ IPF is a debilitating, life limiting condition with a median survival range of 2.5 to 3.5 years from the time of diagnosis.² A study using insurance claims data from the United States estimated the incidence of IPF to be between 6.8 and 16.3 per 100,000 persons.³ The same study yielded a prevalence estimate of between 14.0 and 42.7 per 100,000 persons, depending on the case definition used.³ The economic burden of IPF is significant, with the annual medical cost (hospitalization, emergency room [ER] visits, outpatient visits, and use of procedures and tests) to the US healthcare system estimated at close to \$2 billion in 2012.⁴

The goals of treatment for IPF are to stop disease progression, reduce symptoms, prevent acute exacerbations, and prolong survival.⁵ Pulmonary rehabilitation and oxygen treatment are commonly utilized as supportive treatments, and lung transplant surgery may be considered in some patients.⁵ Many pharmacological treatments (i.e. anticoagulants, combination of N-acetylcysteine, prednisone and azathioprine, selective endothelin receptor) have been evaluated in IPF patients; however, international guidelines recommend against the use of these treatments due to insufficient evidence.⁶ The treatment options for patients with IPF changed significantly in October 2014 when the FDA approved two products that slowed disease progression, Ofev (nintedanib, Boehringer Ingelheim) and Esbriet (pirfenidone, Genentech).^{7,8} Recently updated American Thoracic Society/European Respiratory Society/Japanese Respiratory Society, and Latin American Thoracic Association clinical practice guidelines gave conditional recommendations for the use of nintedanib and pirfenidone in the majority of patients with IPF.⁶

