9.2 SETTING

This retrospective database study will leverage the GE EMR data from October 1, 2013 to April 30, 2018. The EMR consists of patient data from ambulatory care records in the US and is representative of the US population receiving healthcare in the ambulatory setting. Patients will be included in one of three study cohorts based on prescription history from October 1, 2014 to April 30, 2018, allowing for a 12-month pre-index period to describe patient demographic, clinical and treatment characteristics.

Index date

The index date for the nintedanib (or pirfenidone) cohort will be the date of the first nintedanib (or pirfenidone) prescription during the selection window (from October 1, 2014 to April 30, 2018). The index date for the untreated cohort will be the date of the earliest IPF diagnosis or a randomly assigned date between October 1, 2013 and April 30, 2018.

Pre-index period

[figure not shown]
The pre-index period for each cohort will be the 12 months prior to the index date. Patients will be required to have ≥ 1 diagnosis of IPF during the pre-index period (see additional inclusion criteria described below).

Post-index period

The post-index period for each cohort will start from the index date. Since the study aims to evaluate patient characteristics during the pre-index period, no minimum follow-up will be required for post-index period and no study measures will be assess during the post-index period.

Patient selection is illustrated in Figure 1.

Figure 1. Patient Selection

Nintedanib cohort

Inclusion criteria:

- With ≥ 1 diagnosis for IPF (the International Classification of Diseases, Ninth Revision, Clinical Modification [ICD-9-CM] codes 516.3, 516.31, 515,¹¹ or ICD-10-CM codes J84.112) in the EMR between October 1, 2013 to April 30, 2018
- With ≥ 1 prescription for nintedanib between October 1, 2014 and April 30, 2018 (the selection window)
 - The date of the first prescription will be defined as the index date
- With ≥ 1 record in the EMR database during the 12 months prior to the index date (the pre-index period)
- With ≥ 1 diagnosis of IPF during the 12 months prior to the index date
- Age ≥ 40 on the index date
- will explore also requiring ≥ 1 chest CT scan before first IPF diagnosis during the pre-index period¹²

Exclusion criteria:

- With ≥ 1 diagnosis of other known causes of interstitial lung disease (ILD) on the date of or after the first IPF diagnosis during the pre-index period^{12,13}

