- Other known causes of ILD include conditions such as systemic sclerosis, rheumatoid arthritis, systemic lupus erythematosus, dermatomyositis, polymyositis, Sjögren disease, and hypersensitivity pneumonitis (ICD-9-CM codes 135, 237.7, 272.7, 277.3, 277.8, 446.21, 446.4, 495, 500–505, 506.4, 508.1, 508.8, 516.0, 516.1, 516.32–516.37, 516.2, 516.8, 516.9, 517.0, 517.2, 517.8, 518.3, 555, 710.0, 710.0–710.4, 714.0, 714.81, 720, and 759.5, or ICD-10-CM equivalent codes)^{12,13}
- With ≥ 1 prescription for nintedanib prior to the index date
- With ≥ 1 prescription for pirfenidone prior to or on the index date

Pirfenidone cohort

Inclusion criteria:

- With ≥ 1 diagnosis for IPF (ICD-9-CM codes 516.3, 516.31, 515,¹¹ or ICD-10-CM codes J84.112) in the EMR between October 1, 2013 to April 30, 2018
- With ≥ 1 prescription for pirfenidone between October 1, 2014 and April 30, 2018 (the selection window)
 - The date of the first prescription will be defined as the index date
- With ≥ 1 record in the EMR database during the 12 months prior to the index date
- With ≥ 1 diagnosis of IPF during the 12 months prior to the index date
- Age ≥ 40 on the index date
- will explore also requiring ≥ 1 chest CT scan before first IPF diagnosis during the pre-index period¹²

Exclusion criteria:

- With ≥ 1 diagnosis of other known causes of interstitial lung disease (ILD) on the date of or after the first IPF diagnosis during the pre-index period^{12,13}
 - Other known causes of ILD include conditions such as systemic sclerosis, rheumatoid arthritis, systemic lupus erythematosus, dermatomyositis, polymyositis, Sjögren disease, and hypersensitivity pneumonitis (ICD-9-CM codes 135, 237.7, 272.7, 277.3, 277.8, 446.21, 446.4, 495, 500–505, 506.4, 508.1, 508.8, 516.0, 516.1, 516.32–516.37, 516.2, 516.8, 516.9, 517.0, 517.2, 517.8, 518.3, 555, 710.0, 710.0–710.4, 714.0, 714.81, 720, and 759.5, or ICD-10-CM equivalent codes)^{12,13}
- ≥ 1 prescription for pirfenidone prior to the index date
- ≥ 1 prescription for nintedanib prior to or on the index date

Untreated cohort

Inclusion criteria:

- With ≥ 1 diagnosis for IPF (ICD-9-CM codes 516.3, 516.31, 515,¹¹ or ICD-10-CM codes J84.112) in the EMR between October 1, 2013 to April 30, 2018
 - Index date will be defined as the date of the earliest IPF diagnosis or a randomly assigned date based on the exploratory analyses to be performed on the two treatment cohorts (exploring time from IPF diagnosis to treatment initiation)

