9.3.3 Covariates

The following measures will be evaluated during the 12-month baseline period, including index date, unless otherwise noted. Measures will be reported separately for each of the three cohorts.

For nintedanib and pirfenidone cohorts only:

- Index medication (n, %)
 - Nintedanib
 - Pirfenidone
- Average daily dose of the index prescription
 - Nintedanib (mean, SD, median, min, max) and categories (n, %)
 - 100 mg
 - 150 mg
 - Unknown
 - Pirfenidone (mean, SD, median, min, max) and categories (n, %)
 - 267 mg
 - Unknown
- Time from the earliest diagnosis for IPF to index (mean, SD, median, min, max)
- Prescribing physician specialty (n, %)
 - Primary care
 - Internal medicine
 - Pulmonologist
 - Other

For all cohorts:

Demographic characteristics

- Age (mean, SD, median, min, max) and age categories on index date (n, %)
 - 40-49
 - 50-59

- 60-69
 - ≥ 70
- Gender (n, %)
 - Male
 - Female
- Index year (n, %)
 - 2014
 - 2015
 - 2016
 - 2017
 - 2018
- Region (n, %)
 - Northeast
 - Midwest
 - South
 - West
- Race/ethnicity (n, %) (expected to be missing for about 40% of patients)
 - White
 - African American
 - Hispanic
 - Asian
 - Other
 - Unknown
- Payer type (n, %)
 - Commercial
 - Medicaid
 - Medicare
 - Self-Insured
 - Other/Unknown

Clinical characteristics (based on ICD-9/10-CM procedure and diagnosis codes, laboratory test codes, CPT codes and NDC/RxNorm (to be included in Appendix), as well as other information in the EMR encounter files)

- Body weight (lbs; mean, SD, median, min, max)
 - Body mass index (BMI; kg/m²; mean, SD, median, min, max)
 - BMI category, defined using BMI field (n, %)
 - Underweight ($<18.5 \text{ kg/m}^2$)
 - Normal weight (18.5 to 24.99 kg/m²)
 - Overweight (25 to 29.99 kg/m²)
 - Obese (30 to 34.99 kg/m²)
 - Very obese ($\geq 35 \text{ kg/m}^2$)

- Blood pressure (BP)¹⁴ (n, %)
 - Diastolic BP
 - Normal (<80 mmHg)
 - High (≥ 80 mmHg)
 - Systolic BP
 - Normal (<120 mmHg)
 - Elevated (≥ 120 and < 129 mmHg)
 - High (≥ 130 mmHg), further broken down as follows if data allow
 - Stage 1 (≥ 130 and < 139 mmHg)
 - Stage 2 (≥ 140 mmHg)
- Smoking status at index (n, %); excluding smokeless tobacco; categories to be finalized during analysis
 - Smoker
 - Non-smoker, further broken down as follows if data allow
 - Previous smoker
 - Never smoker
 - Unknown/missing
- Alcohol consumption (n, %)
 - Yes
 - No
 - Unknown/missing

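### Time from IPF diagnosis to treatment is truncated on either reading of the plan: at 12 months for everyone, or at a data-start ceiling that rises from 12 to about 55 months with index date

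*Combined protocol and SAP*

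**What the plan says.** Section 9.3.3 opens with a default window: "The following measures will be evaluated during the 12-month baseline period, including index date, unless otherwise noted". For the two treated cohorts it then lists "Time from the earliest diagnosis for IPF to index (mean, SD, median, min, max"), with no separate look-back. The abstract (section 4) says its listed characteristics "during the 12-month baseline period (pre-treatment) will be evaluated and compared between cohorts", and that list includes "time from the earliest diagnosis of IPF to index medication".

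Section 9.2 sets the extract: "This retrospective database study will leverage the GE EMR data from October 1, 2013 to April 30, 2018". Treated index dates run from October 1, 2014 to April 30, 2018. A treated patient needs at least one IPF code in the 12 months before index. Nothing requires that code to be the patient's first, and there is no diagnosis-free run-in.

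For untreated patients, section 9.2 offers two index dates. One is the day of the first IPF code; the alternative is described as "randomly assigned date based on the exploratory analyses to be performed on the two treatment cohorts (exploring time from IPF diagnosis to treatment initiation").

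The primary outcome (section 9.3.2.1) is the ASD and p-value for the section 9.3.3 characteristics, and section 9.7.1 treats an ASD of 10% or more as meaningful. The abstract also plans a stratified description at different time points. The limitations in section 9.9 do not mention look-back or truncation.

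**The concern.** The item is meant to show how long patients had carried the diagnosis when they started treatment. It can do that only if the first diagnosis is visible. Section 9.3.1 dates both approvals to October 15, 2014, and section 7 gives a "median survival range of 2.5 to 3.5 years from the time of diagnosis". Patients diagnosed more than 12 months before an early index date are therefore plausible. For them the earliest visible code is a follow-up code and the recorded interval is too short.

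Three results are exposed. The nintedanib versus pirfenidone ASD for this item may be compressed, or under the other reading shifted. The description over calendar time may show an interval that lengthens only because more history becomes visible. If untreated index dates are drawn from the treated delay distribution, they would come from a truncated distribution.

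**Working it through.** **1. Ceiling implied by the dates.** Inputs are from section 9.2. Ceiling = index date minus October 1, 2013, in months of 30.4375 days.

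| Index date | Literal 12-month window | Whole extract |
|---|---|---|
| October 1, 2014 | 12 | 12.0 |
| October 1, 2015 | 12 | 24.0 |
| October 1, 2016 | 12 | 36.0 |
| October 1, 2017 | 12 | 48.0 |
| April 30, 2018 | 12 | 54.9 |

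The plan's own 12 months of history before the first possible treated index date is reproduced. This step needs no assumption.

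**2. Share beyond 12 months (assumed delays).** The documents give no delay distribution. I assume exponential delays with mean μ. Then P(T > 12) = exp(−12/μ), and the mean of min(T, 12) is μ(1 − exp(−12/μ)).

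| μ (months) | Beyond 12 months | Capped mean |
|---|---|---|
| 6 | 14% | 5.2 |
| 12 | 37% | 7.6 |
| 24 | 61% | 9.4 |

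**3. Flat cap and the drug comparison.** The ASD uses the section 9.7.1 formula. An exponential SD equals its mean, so for true means of 18 and 24 the uncapped ASD is 6/√((18² + 24²)/2) = 0.28. After capping, the means are 8.76 and 9.44 and the SDs 4.10 and 3.84, giving 0.68/3.97 = 0.17.

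| True means | True ASD | Capped ASD |
|---|---|---|
| 6 vs 9 | 0.39 | 0.35 |
| 12 vs 15 | 0.22 | 0.16 |
| 18 vs 24 | 0.28 | 0.17 |
| 24 vs 30 | 0.22 | 0.12 |

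With equal true delays the flat cap gives an ASD of about 0, so it hides differences but does not create them.

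min(T, 12) records exactly 12 months for a long-diagnosed patient. A follow-up code would record 12 or less. If such a patient has k codes spread evenly at random over the window, the earliest lies on average 12k/(k + 1) months before index: 6, 8 or 9.6 months for k = 1, 2 or 4. For true means of 18 vs 24 the ASD is then 0.04, 0.09 or 0.14, so compression can be stronger than the table shows.

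**4. Data-start ceiling and calendar time.** I keep the true mean constant and spread index dates evenly, with ceilings of 12–27 months (first 15 months of selection) and 27–55 months (the rest).

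| μ | Early mean | Later mean | Spurious ASD |
|---|---|---|---|
| 6 | 5.7 | 6.0 | 0.05 |
| 12 | 9.5 | 11.5 | 0.23 |
| 24 | 13.2 | 19.4 | 0.55 |

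**5. Data-start ceiling and the drug comparison.** With equal true delays, a false difference needs different calendar uptake. If one drug's index dates average 6 months later, the spurious ASD is 0.06, 0.10 and 0.13 for μ = 12, 18 and 24. For a 12-month shift it is about 0.10, 0.19 and 0.26. At the preliminary counts of 615 and 868, the 95% CI half-width for an ASD is 1.96 × √(1483/(615 × 868)) = 0.10.

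**The case against.** The strongest reply is that the 12-month cap is not the only reading. Where section 9.2 wants a first diagnosis confined to the pre-index period, it says so; the section 9.3.3 item says only earliest. Row 4 of Table 1 counts diagnoses before index with no 12-month limit. Neighbouring items, such as index dose and prescriber specialty, are index-date facts, so the header rule is applied loosely. This stands: the cap is the literal text, supported by the abstract, but the team may not have intended it. It does not remove the problem, because the looser reading leaves the data-start ceiling.

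A reader might go further in four ways that the documents do not support:

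- **A biased drug comparison as a certainty.** A flat cap creates no false difference. The data-start ceiling does so only if uptake differs over time. Both drugs were approved on the same day, and no index dates by drug are given.
- **Untreated index dates placed too close to diagnosis.** The random date is one of two options. Its exploratory analysis sits in section 9.2, outside the section 9.3.3 window rule. Untreated patients' earliest diagnosis is limited by the same data start. Only inheritance of the data-start truncation follows.
- **Time since diagnosis as the plan's main marker of disease stage.** Section 9.3.3 gives that role to pulmonary function tests and also lists GAP stage. This interval is one of many items.
- **A known share of early initiators diagnosed long before.** The survival range makes such patients plausible; it does not count them.

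The plan also reports index year and a description over time, which would help a reader see the artefact. Neither compares this interval between drugs within index year.

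**Conclusion.** The concern holds in limited form. On either reading, the planned mean, SD, median and ASD for this item describe a truncated interval, and section 9.9 is silent. The ceilings of 12 months, or 12 to about 55 months, follow from the plan's dates alone. The direction depends on the reading: compression under the flat cap; under the data-start ceiling, an artificial rise with index year, plus a false drug difference only if uptake differs.

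The amount of distortion cannot be computed from the documents. The figures above rest on exponential delays and evenly spread index dates, neither of which comes from the plan. They range from negligible (mean delays near 6 months) to well above the 10% threshold. In the 18 versus 24 month example the simple cap leaves the ASD above 10%, so that classification would not change; with only one or two follow-up codes per patient it would. This is a point the plan should correct, not one that undermines the study as a whole.

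**What to change.** - In section 9.3.3, exempt this item from the 12-month window and define it from all EMR records available before index, including before October 1, 2013 if they can be obtained. Section 9.4 describes longitudinal records but does not show that earlier data are available for these patients.
- Report each patient's available look-back, and flag as left-truncated those whose first IPF code falls close to their start of observation.
- Report the interval in categories that can be resolved for everyone, for example under 3, 3–6, 6–12, and over 12 months or unknown. Compare the drugs within index year.
- If the random-date option is chosen, derive the untreated index-date distribution only from treated patients with an observed incident diagnosis.
- List residual left truncation in section 9.9.

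The cost is protocol wording and, if earlier records exist, a wider query on diagnosis dates. Some patients will have a category instead of a number, and the subset with an observed incident diagnosis will be smaller.

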 - Carbon monoxide diffusing capacity of the lung (DLCO; n, %)

- Normal (>75% of predicted)
- Mild to moderate decrease (40-74% of predicted)
- Severe decrease (<40% of predicted)
- Oxygen saturation (n, %)
 - Normal (95-100%)
 - Below normal (<95%)
- GAP index¹⁸ (n, %), if data allow
 - Calculated using information on age, gender and FVC
 - Stage I (0-3 points)
 - Stage II (4-5 points)
 - Stage III (6-8 points)

Treatment history during the pre-index period (not including index date):

- Pharmacological interventions (n, %)
 - Other treatments (as per ATS/ERS/JRS/ALAT guidelines¹⁹)
 - Selective tyrosine kinase inhibitor against platelet derived growth factor (Imatinib)
 - Prednisone
 - Azathioprine
 - N-acetylcysteine
 - Selective endothelin receptor antagonist (ambrisentan)
 - Phosphodiesterase-5 inhibitor (sildenafil)
 - Dual endothelin receptor antagonists (macitentan, bosentan)
 - Corticosteroids
 - Inhaled corticosteroids
 - Oral corticosteroids
 - Bronchodilators
 - SABA
 - LABA
 - Anticholinergics
 - Other beta agonists
 - GERD therapy
 - H-2 receptor blockers
 - Proton pump inhibitors
 - Antacids
 - Cardiovascular drugs
 - Antianginals
 - Antihypertensives
 - Antiarrhythmics
 - Antiplatelets
 - Anticoagulants

- Antidiabetes drugs
- Anti-infectives
- Anticonvulsants
- Anti-anxiety drugs
- Antidepressants
- Antipsychotics
- Antihyperlipidemics
- Non-pharmacological interventions (n, %)
 - Surgical procedures (n, %)
 - Lung transplantation
 - Esophageal sphincter reinforcement
 - Lung cancer surgeries
 - Supportive therapy (n, %)
 - Oxygen therapy
 - Pulmonary rehabilitation
 - Diagnostic procedures (n, %)
 - High resolution computed tomography (HRCT)
 - Surgical lung biopsy
 - Chest X-rays
 - 6-minute walk test/pulmonary stress test
 - Spirometry
 - Bronchoalveolar lavage

Treatment on the index date (pharmacological interventions only):

- For each of the following treatments, the number and proportion of patients with and without the treatment on the index date will be reported (days' supply to be considered when exploring treatment use on index)
 - Other treatments (as per ATS/ERS/JRS/ALAT guidelines¹⁹; n, %)
 - Selective tyrosine kinase inhibitor against platelet derived growth factor (Imatinib)
 - Prednisone
 - Azathioprine
 - N-acetylcysteine
 - Selective endothelin receptor antagonist (ambrisentan)
 - Phosphodiesterase-5 inhibitor (sildenafil)
 - Dual endothelin receptor antagonists (macitentan, bosentan)
 - Corticosteroids (n, %)

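### If untreated patients get a random index date, counting the index day in the baseline can tilt diagnosis-code, Charlson and any-history laboratory flags upward in the treated cohorts

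*Combined protocol and SAP*

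**What the plan says.** Section 9.3.3 sets the default window for covariates: "The following measures will be evaluated during the 12-month baseline period, including index date, unless otherwise noted". Section 9.2 describes the pre-index period differently: "The pre-index period for each cohort will be the 12 months prior to the index date". It does not say that the index day belongs to that period.

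For both treated cohorts, section 9.2 says: "The date of the first prescription will be defined as the index date". For the untreated cohort it leaves two options: "The index date for the untreated cohort will be the date of the earliest IPF diagnosis or a randomly assigned date". The Index date paragraph describes the second option as "a randomly assigned date between October 1, 2013 and April 30, 2018". The untreated inclusion criteria describe it as "a randomly assigned date based on the exploratory analyses to be performed on the two treatment cohorts". Nothing requires the random date to fall on a visit.

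Section 9.3.3 makes an exception for treatment history, which covers drugs, surgery, supportive therapy and diagnostic procedures: "Treatment history during the pre-index period (not including index date". Drug use on the index day has its own table: "Treatment on the index date (pharmacological interventions only". There is no such exception for the ICD-based comorbidities, the Charlson index or the laboratory rows. For ALT, AST, total bilirubin, GFR and serum creatinine, any abnormal result in the baseline overrides the value nearest to index.

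**The concern.** A prescription date is plausibly a day on which diagnoses are coded and tests recorded. A random calendar date is such a day only by chance. Take two patients with the same disease and the same visit habit. Under the random-date option the treated one can contribute one more coded contact than the untreated one. An indicator that turns positive on any single record can only go up with an extra contact, so the tilt always runs the same way. It also raises the Charlson index, which is built from such indicators.

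The primary outcome (9.3.2.1) is the absolute standardized difference (ASD) with a p-value, and 9.1 and 9.7.1 treat an ASD of 10% as meaningful. Section 9.7.1 uses p-values to help identify what drives treatment choice, and bivariate significance is one route into the logistic model. An artefact of the index rule could therefore be reported as greater comorbidity in treated patients and carried into the treated-versus-untreated propensity score.

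**Working it through.** The documents give no figure for this effect, so there is none to reproduce. What follows is an illustration under stated assumptions.

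**Inputs from the documents.** Preliminary cohort sizes (Abstract, study size): nintedanib 615, pirfenidone 868, untreated about 10,000; pooled treated 615 + 868 = 1,483. The ASD and confidence interval formulas are those of 9.7.1. The threshold is 0.10 and alpha is 0.05, two-sided.

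**Assumptions.** Each patient has k visits in the 12 months before index, and q is the chance that a code is entered at a visit. Neither is given in the documents.

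**Step 1: chance that a random day is a visit.** k/365: 4/365 = 1.1%; 12/365 = 3.3%; 20/365 = 5.5%.

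**Step 2: same q for every patient, every prescription date a coded visit.**

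- Untreated, random date: p = 1 − (1 − q)^k × (1 − q·k/365)
- Treated, one extra contact: p = 1 − (1 − q)^(k+1)

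For k = 4, q = 0.10: untreated 1 − 0.6561 × 0.9989 = 0.345; treated 1 − 0.9^5 = 0.410. ASD = (0.4095 − 0.3446) / √[(0.4095 × 0.5905 + 0.3446 × 0.6554)/2] = 0.134. The 95% CI is 0.053 to 0.216 with 615 treated and 0.065 to 0.204 with 868.

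Artificial ASD with no true difference:

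| Visits k | q = 0.02 | 0.05 | 0.10 | 0.20 | 0.30 |
|---|---|---|---|---|---|
| 2 | 0.088 | 0.138 | 0.192 | 0.260 | 0.300 |
| 4 | 0.065 | 0.100 | 0.134 | 0.169 | 0.178 |
| 6 | 0.053 | 0.080 | 0.105 | 0.122 | 0.116 |
| 8 | 0.046 | 0.068 | 0.086 | 0.092 | 0.079 |
| 12 | 0.036 | 0.052 | 0.062 | 0.055 | 0.037 |

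**Step 3: persistent conditions.** Let a share P have the condition, coded at a fraction s of their visits, and ignore the roughly 1% chance visit. Untreated: P[1 − (1 − s)^k]. Treated: P[1 − (1 − s)^(k+1)]. With k = 4:

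| P | s | Untreated | Treated | ASD |
|---|---|---|---|---|
| 20% | 50% | 18.8% | 19.4% | 0.016 |
| 40% | 50% | 37.5% | 38.8% | 0.026 |
| 40% | 30% | 30.4% | 33.3% | 0.062 |
| 60% | 30% | 45.6% | 49.9% | 0.087 |
| 60% | 20% | 35.4% | 40.3% | 0.10 |

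At six visits the first three rows fall to 0.004, 0.006 and 0.029. At two visits some cells pass 0.10: P = 40%, s = 30% gives 20.4% against 26.3%, ASD 0.139.

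**Step 4: only a fraction f of prescription dates are coded visits.** For k = 4, q = 0.10, treated p = 1 − 0.9^4 × (1 − f × 0.10). ASD is 0.134 at f = 1, 0.101 at 0.75, 0.067 at 0.50 and 0.033 at 0.25.

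**Step 5: the p-value route** (normal approximation, two proportions).

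- Step 2 model, k = 8, q = 0.10 (ASD 0.086): chance of p < 0.05 is about 0.54 for nintedanib, 0.67 for pirfenidone and 0.87 for the pooled treated group, each against 10,000.
- Step 3 row with ASD 0.062: about 0.6 for the pooled group.

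**Step 6: after the change.** With the index day removed from these flags in all three cohorts, both groups have the same k contacts and the artificial ASD is 0 in every cell.

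**The case against.** The strongest objection is to the size. Step 2 gives every patient the same chance of a code at each visit. Most comorbidities listed in 9.3.3 are conditions that a patient either has or does not have, such as diabetes, COPD or heart failure, and for these step 3 gives much smaller values. This stands. The larger values suit transient codes such as cough or sinusitis, or persistent conditions coded thinly in patients with few visits.

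It can also be said that the documents require a prescription record, not a coded encounter that day. This stands too, and step 4 shows what it does to the size.

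A third objection is that the untreated index rule is still open and the earliest IPF diagnosis is listed first. Under that option the untreated index day itself carries a diagnosis record, and the asymmetry largely disappears. The point is therefore conditional.

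A reader might infer that every baseline flag is tilted. The text does not support that. Treatment history, including procedures, already leaves out the index day. Weight, blood pressure and most laboratory tests are reported as values or categories, with the result nearest to index used for repeated tests. Patients without a value are left out of that comparison (9.7.1). For those rows the index day affects availability and recency, not an upward count. Nintedanib versus pirfenidone is also untouched, because both cohorts are indexed on a prescription.

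None of this removes the asymmetry for the remaining rows if the random date is chosen.

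**Conclusion.** The point holds in a limited, conditional form. If the untreated index is a random date not tied to a visit, the default window in 9.3.3 tilts the ICD-based comorbidities, the Charlson index and the five any-history laboratory rows upward in the treated cohorts. It does so in both untreated contrasts and in the treated-versus-untreated propensity model.

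The size is unknown because the documents give no visit frequency or coding rate. At four assumed visits the artificial ASD runs from under 0.02 to about 0.17. Two visits would give more. At eight or more visits no cell in the step 2 table reaches 0.10. A reader might take 0.14 to 0.17 as the expected bias, but that needs few visits, equal coding chances for all patients and a coded visit on every prescription date. Below the 10% line the artefact can still matter, because with about 10,000 untreated patients a small tilt may reach p < 0.05 and so enter the driver screen and covariate selection.

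**What to change.** If a random untreated index date is used, end the window for diagnosis-code flags, the Charlson index and the any-history laboratory flags on the day before index in all three cohorts. This is the rule that 9.3.3 already applies to treatment history. Reconcile the opening sentence of 9.3.3 with the definition of the pre-index period in 9.2, so that one statement governs whether the index day counts.

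The cost is a line of text and one programming step. The change itself removes no patients from the cohorts. The small downside is that conditions first coded on the index day are not counted.

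Moving the untreated index to the next encounter after the random date would also make it a clinical contact, but it is not preferred. It selects untreated patients who survive and stay in care, in a disease for which section 7 gives a median survival of 2.5 to 3.5 years.
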